### 13.2. General Statistical Considerations and Definitions

#### 13.2.1. General Statistical Methods

As a general approach, continuous variables will be summarized using mean, standard deviation, median, minimum value, and maximum value. Categorical variables will be summarized using frequency counts and percentages. Time to event data will be summarized using the Kaplan-Meier method. Where appropriate, CIs around point estimates will be presented, and estimates of the median and other quantiles, as well as individual time points (for time to event data) will be produced.

All statistical hypothesis testing within (for change from baseline) and between dose cohorts will be conducted at the 1-sided 0.05 level of significance. Nominal p-values may be computed for secondary or exploratory efficacy analyses as a descriptive measure of strength of results rather than for formal tests of hypotheses. Emphasis will be on RP2D, highest dose, and combined RP2D and all higher doses for change from baseline and comparison to lowest dose. No formal tests of hypotheses are planned for safety analyses.

The following methods will be used in this trial for descriptive summaries and hypothesis testing unless otherwise indicated:

- **Mean change from baseline.** Compared to zero change and compared between dose levels using t-tests from repeated measures as the analysis model and/or via non-parametric tests based on ranks, as appropriate.
- **Median time to event for a single group (non-comparative).** The Kaplan-Meier method will be used to estimate median time to event; 2-sided CIs will use the method of Brookmeyer and Crowley; p-values will not be computed.
- **Hazard ratio of a time to event endpoint comparing two groups.** A stratified Cox proportional hazards model using Efron's method for ties will be used to estimate the HR and 2-sided CI; p-values will be computed using the log rank test.

- **Time to event analysis at a fixed time point.** The Kaplan-Meier method will be used to estimate the survival (or event-free) probability; 2-sided CIs for a single survival probability or for a difference of two survival probabilities will use the complementary log-log method; p-values will be computed using the complementary log-log test statistic.

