### **13.3.3.3. Analysis of Duration of Biomarker Response**

Duration of biomarker response (ie, reduction or clearance) will be reported for subjects who meet the biomarker reduction or clearance definitions.

- Duration of biomarker reduction is calculated from the date of the first biomarker blood test with a reduction compared to baseline, until the earliest date of any of the following events: (1) subsequent increase in biomarker; (2) subsequent disease recurrence; or (3) death due to any cause.
- Duration of biomarker clearance is calculated from the date of the first negative ctDNA test or the date when the serum tumor biomarker is  $\leq$ ULN to the earliest date of any of the following events: (1) subsequent positive ctDNA test or subsequent serum tumor biomarker  $>$ ULN; (2) subsequent disease recurrence; or (3) death due to any cause.

If a subject has not experienced any of the events for reduction or clearance, duration of response will be censored on the date of the last biomarker assessment.

Response duration will be summarized for each cohort. Assessment of biomarker response duration is considered supportive of the primary biomarker response analysis and is not considered part of the fixed sequence testing procedure to control overall type 1 error.

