
Clearance
	
Define as the percent change from baseline of the on-study ctDNA, or CA19-9, or CEA that achieved -100%.
 
Notes:
 
 
a. Clearance start will be the date of first clearance.
 
b. Once clearance start date is identified for a biomarker, the same biomarker will be used to determine the clearance end date.
 
c. Results will not be considered if a subject has already started taking subsequent anti-cancer therapy.
 
d. If there is a tie for best response across biomarkers, select ctDNA first.                             
 
▪ For PDAC subjects, select CA19-9 second, CEA third.
 
• For CRC subjects, select CEA second, CA19-9 third.
 
 
 

Reduction
	
Defined as the percent change from baseline of the on-study ctDNA, or CA19-9, or CEA that achieved any decrease (i.e., a negative percent change from baseline).
 
Notes:
 
 
a. Reduction start will be the date of first reduction.
 
b. Once reduction start date is identified for a biomarker, the same biomarker will be used to determine the reduction end date.
 
c. Results will not be considered if a subject has already started taking subsequent anti-cancer therapy.
 
d. If there is a tie for best response across biomarkers, select ctDNA first.                             
 
• For PDAC subjects, select CA19-9 second, CEA third.
 
• For CRC subjects, select CEA second, CA19-9 third.
 
 
 

Duration of Biomarker Clearance/Reduction
	

Clearance Duration
	
This is confirmed after clearance start by an increase above -100% change from baseline followed by a second increase above -100% at least 1 week afterwards.
 
Notes:
 
 
a. The end date will be the date of the first subsequent increase.
 
b. If the increase cannot be confirmed by a second increase, then the potential end date of biomarker clearance will proceed to the next increase and so on.
 
c. Subjects with confirmed clearance duration will not be censored.
 

Reduction Duration
	
This is confirmed after reduction start by an increase above the initial reduction followed by a second increase above the initial reduction at least 1 week afterwards.

**Final Analysis  

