## 2.2. ctDNA

ctDNA response is defined as the absence or reduction of circulating tumor DNA post-baseline. Analysis of ctDNA will be based on results from two laboratories and will be performed separately.

Duration of response is defined as the time in weeks from reduction until the date of increase or presence of ctDNA.

Any patient with detectable ctDNA at baseline whose post-baseline result is less than the baseline value or undetectable will be considered a responder. The number and percentage of responders will be reported.

Doubling will be calculated as the number of weeks between visits where ctDNA first doubles.

Doubling time and response will be based on the tumor molecules per mL (MTM/mL) and Variant Allele Frequency (VAF).

ctDNA levels over time will be summarized using descriptive statistics.

Data listings will present ctDNA values (VAF and MTM/mL) over time, ctDNA response, and duration of response, and time until doubling of ctDNA.

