DATE: HH:MM/DDMMYY

Protocol ELI-002-001                      Elicio Therapeutics, Inc.                      Confidential                      Page 1 of x

Table 7  
 Summary and Change from Baseline for ctDNA (ctDNA  
 Population)

Baseline	Baseline (1)	Cohort 1 (N=xx)	Cohort 1 (N=xx)	Cohort 1 (N=xx)
		N (2)	xx	--
		Mean (SD)	xx.x (xx.xx)	
		Median Min,	xx.xx xx.x	
		Max	xx.x	
		N Undetectable (3)	xx.x, xx.x xx	
		<repeat for remaining visits with at least 3 subjects		
Visit 6		N (2)	xx	xx
		Mean (SD)	xx.x (xx.xx)	xx.x (xx.xx)
		Fold Change Mean	xx.xx	xx.xx
		Fold Shange SD- SD	xx.x	xx.x
		Median	xx.x	xx.x
		Min, Max	xx.x, xx.x	xx.x, xx.x
		N Undetectable (3)	xx	xx
Doubling Time	N(4)	Mean (SD)		
		Median		
		Min, Max		
Clearance Duration (weeks)	N(5)	Mean (SD)		
		Median		
		Min, Max		
Response Rate	n%			

[1] Baseline is based on Visit 3 result or Visit 2 if Visit 3 is missing  
 [2] N reflects the number of patients with detectable concentrations of ctDNA .

[3] Number of subjects with results below the limit of detection. [4] N reflects the subjects whose ctDNA doubled.

[5] N reflects subjects whose ctDNA was undetectable or decreased post-baseline.

[REPEAT univariate statistics For VAF + MTM/ML by Assay]

Notes for programming: Timepoints –

- Visits 2, 3 (pre-vaccination)
- Visits 6, 11, 12, 16, 17, 18, 19, 20, 21, 22, 23, 24 (post-vaccination)

Elicio Therapeutics, Inc.  
Protocol ELI-002-001

Confidential

[figure not shown]
Page 1 of x

Figure 1

Ex vivo Fluorospot

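### The clearance-duration row in Addendum Table 7 counts every ctDNA responder and has no rule for responses still ongoing

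*SAP*

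**What the plan says.** **Addendum, Table 7 shell.** There is one duration row, labelled as clearance duration in weeks. Its statistics are N, mean (SD), median, and minimum and maximum. Footnote 5 defines the N: "N reflects subjects whose ctDNA was undetectable or decreased post-baseline".

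**Addendum section 2.2.** A responder is any subject with detectable ctDNA at baseline whose later result is lower or undetectable. "Duration of response is defined as the time in weeks from reduction until the date of increase or presence of ctDNA". The note under Listing 7 words the end differently: duration stops when ctDNA can be detected or exceeds its baseline value. Neither place says what to do with a response that has not ended.

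**Protocol section 13.3.3.3.** Two durations are defined. "Duration of biomarker reduction is calculated from the date of the first biomarker blood test with a reduction compared to baseline"; "Duration of biomarker clearance is calculated from the date of the first negative ctDNA test". Both can also end at disease recurrence or death. If none of the end events has occurred, "duration of response will be censored on the date of the last biomarker assessment".

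**Protocol section 13.2.1.** "Time to event data will be summarized using the Kaplan-Meier method".

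**SAP Table 8.** Clearance and reduction have separate entries and separate duration entries. Clearance reads: "Define as the percent change from baseline of the on-study ctDNA, or CA19-9, or CEA that achieved -100" per cent. The duration entries require the end to be confirmed by a second rise at least one week later. They state that subjects with a confirmed end are not censored, which implies that the others are.

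**SAP section 14.0.** ctDNA analyses are declared outside the main SAP and referred to the Addendum.

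**The concern.** The label and the content of the row disagree. A reader of the study report would take the figure as how long ctDNA stayed undetectable, while the footnote admits subjects whose ctDNA fell but never became undetectable. Under the protocol such subjects have a reduction duration and no clearance duration.

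The statistics are also unsuited to the data. A duration with ongoing responses is a censored time-to-event variable. A mean and SD cannot carry censored values, so the programmer must either drop the ongoing responses or treat the last test date as the end. The Addendum does not say which, and the two choices give different numbers.

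At stake is a descriptive figure that may inform later studies of this vaccine. No test, sample size or dose decision rule depends on it.

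**Working it through.** The documents give no duration data and no planned figure for this row, so there is nothing to reproduce. The check has three parts.

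**1. Who enters the row.** The population in footnote 5 (undetectable or decreased) is the responder definition of Addendum 2.2. The protocol's clearance duration starts at a first negative test, and SAP Table 8 needs a 100 per cent fall. A decrease-only subject meets footnote 5 and fails both of the others. The row therefore holds response duration under a clearance label.

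**2. What the end rule does to a decrease-only subject.** Let the baseline be B and the first lower value be x, with 0 < x < B. The response starts on the date of x.
- Listing 7 note: the end is the date ctDNA is detectable or above baseline. At x it is already detectable, so end = start and the duration is zero.
- Addendum 2.2: the end is an increase or the presence of ctDNA. It is present at x, so the same problem arises.
- If the programmer looks only at later tests, the next detectable result ends the response even if it is still falling. For a response first seen at Visit 6 (week 3) with the next scheduled ctDNA test at Visit 11 (week 17), the duration would be 17 − 3 = 14 weeks, set by the visit schedule.
- Protocol 13.3.3.3: the reduction continues until a subsequent increase, recurrence or death.
- SAP Table 8: it continues until a confirmed rise above the initial reduction.

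Recurrence and death end the duration in the protocol and in SAP section 9.1.3, but appear in neither Addendum rule.

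**3. What a simple mean does with ongoing responses (illustration only).** Assume exponential durations with rate λ = ln 2 / median, and a common follow-up F after response.
- True mean = 1/λ.
- Fraction ongoing = exp(−λF).
- Mean with ongoing responses cut at F = (1 − exp(−λF))/λ, which is the true mean × the fraction ended.
- Mean of ended responses only = (cut mean − F·exp(−λF)) / (1 − exp(−λF)).

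Worked case, median 52 and F = 52 weeks: the true mean is 75.0 and half are ongoing. The cut mean is 75.0 × 0.5 = 37.5. The ended-only mean is (37.5 − 52 × 0.5)/0.5 = 23.0.

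The medians and follow-up times below are assumptions. The 106 weeks is roughly Visit 6 (week 3) to Visit 24, where Table 7 stops: (819 − 57)/7 = 108.9, less 3.

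| True median (mean), weeks | F, weeks | Ongoing | Cut mean | Ended-only mean |
|---|---|---|---|---|
| 26 (37.5) | 26 | 50% | 18.8 | 11.5 |
| 26 (37.5) | 52 | 25% | 28.1 | 20.2 |
| 26 (37.5) | 106 | 6% | 35.3 | 30.8 |
| 52 (75.0) | 26 | 71% | 22.0 | 12.3 |
| 52 (75.0) | 52 | 50% | 37.5 | 23.0 |
| 52 (75.0) | 106 | 24% | 56.8 | 40.9 |
| 104 (150.0) | 26 | 84% | 23.9 | 12.6 |
| 104 (150.0) | 52 | 71% | 43.9 | 24.5 |
| 104 (150.0) | 106 | 49% | 76.0 | 46.8 |

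Both simple means fall below the true mean in every case, by little when few responses are ongoing and by a lot when many are.

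The same happens in a small invented cohort of six, with responses ended at 8, 17 and 26 weeks and ongoing at 46, 88 and 102:
- Ended-only mean: (8 + 17 + 26)/3 = 17.0.
- All six cut at last test: 287/6 = 47.8, with a simple median of 36.0.
- Kaplan-Meier: falls to 5/6, then 4/6, then 3/6 at week 26 and stays at 0.50, with three of six shown as ongoing.

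**The case against.** Four points on the other side carry weight.

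- **A pooled duration is not foreign to the plan.** The exploratory endpoint in Protocol 6.2.3 and SAP 9.1.3 runs from the first negative and/or decreased biomarker, and Protocol 13.3.3.3 speaks of response duration by cohort. A reader might infer that the protocol forbids pooling; it does not. This supports a pooled row under an honest label. It does not support calling that row clearance.
- **The main SAP already separates the two and implies censoring.** Table 8 does so, the revision history lists these definitions as new in version 3.0 (2024), and SAP 13.6 offers Kaplan-Meier estimates where relevant. It would be wrong to conclude that the plan nowhere handles this. But the attached Addendum is still version 1.0 of February 2023, section 14.0 still refers ctDNA analyses to it, and SAP Table 15 names Kaplan-Meier only for RFS, 1-year RFS and OS. The older shell has not been reconciled.
- **The Addendum is silent on ongoing responses.** It does not say that they are dropped or counted as ended, and a claim that it ignores them by design goes beyond the text. The gap remains, because mean (SD) forces one choice or the other.
- **The stakes are small.** Duration is exploratory, Listing 7 will show each subject's value, and Kaplan-Meier estimates in cohorts of 3 to 6 will be imprecise. All of this stands. It limits the importance of the point without making the row right.

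**Conclusion.** The point holds as an inconsistency between the Addendum and both the protocol and SAP Table 8. Run as written, the shell gives a figure labelled clearance that includes decrease-only responders, uses an end rule that breaks down for those subjects, and has no means of handling censored durations. Section 14.0 explains the dropping of formal tests and confidence intervals for most efficacy analyses. It does not declare this departure.

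The size is unknown. A reader might infer that most contributors never cleared, or that the reported mean would be half the true one. The documents support neither. They give no count of cleared or ongoing subjects, and they do not say when long-term follow-up was stopped. The factor of one half arises only if durations are exponential, censoring is independent, exactly half of the responses are ongoing, and those are cut at the last test. The direction (downward for the mean) holds throughout the illustrated range, but that range rests on the same exponential model. Only the reported duration is affected.

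**What to change.** - Replace the row in Addendum Table 7 with two: clearance duration for subjects whose ctDNA became undetectable, and reduction duration for subjects with any decrease. Amend footnote 5 to match.
- Align the start and end events in Addendum 2.2, Table 7 and the Listing 7 note with Protocol 13.3.3.3 and SAP Table 8. Add recurrence and death as end events. State whether the end needs the confirmation that Table 8 requires and the protocol does not.
- Censor ongoing responses at the last biomarker assessment.
- Report Kaplan-Meier estimates with the number censored, pooled across cohorts where a cohort is too small, and drop the mean (SD).
- State in section 14.0 which definition governs ctDNA duration.

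The cost is one extra table row, a standard procedure call and a short revision of the Addendum. The estimates in small cohorts will be imprecise and some medians may not be reached. The number censored makes that visible.

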**EXAMPLE**

Repeat layouts for all figures. Each cohort will be identified by different colors on the scatter plot. All parameters included in summary tables should be graphed.

Protocol ELI-002-001 Elicio Therapeutics, Inc Confidential Page 1 of x

Listing 1  
 Ex vivo Fluorospot

Dose Cohort:

Patient ID	KRAS / NRAS	Visit/ Week (1)	Date	Antigen	Analyte	Result(2)	Change from baseline	Fold change from baseline	Response Based on DFR
------------	-------------	--------------------	------	---------	---------	-----------	----------------------	------------------------------	--------------------------

(1) Relative to first dose date.  
 (2) Response is based on bootstrap method described by Moodie (2010) testing for 2-fold difference from the control wells  
 (3) IVS Fluorospot results reflect the mean of background-subtracted replicate results. Ev Vivo Fluorospot results reflect the average of normalized background-subtracted replicate results.

Programming note - NS antigen is not included in the table but should be included in listing.

Protocol ELI-002-001

Elicio Therapeutics, Inc

Confidential

Page 1 of x

Listing 2  
In Vitro Fluorospot

Repeat Listing 1 layout using data from IVS Fluorospot.

Protocol ELI-002-001 Elicio Therapeutics, Inc Confidential Page 1 of x

Listing 3  
 Ex Vivo Intracellular Cytokine Staining

KRAS / NRAS		Change from	Fold change from				
Patient ID	Mutation	Visit Date	Antigen	Test	Result	baseline	baseline
						Live cells	
						Lymphocytes	
						CD3 T cells	
						CD4 T cells	
						CD4 IFNg	
						CD4 IL2	
						CD4 TNFa	
						CD4 Cm	
						CD4 Cm IFNg	
						CD4 Cm IL2	
						CD4 Cm TNFa	
						CD4 Em	
						CD4 Em IFNg	
						CD4 Em IL2	
						CD4 Em TNFa	
						CD4 Naive	
						CD4 Naive IFNg	
						CD4 Naive IL2	
						CD4 Naive TNFa	
						CD4 TEMRA	
						CD4 TEMRA IFNg	
						CD4 TEMRA IL2	
						CD4 TEMRA TNFa	
						CD4 IFNg-	
					DMS	CD4 IL2-	
					O	CD4 TNFa-	
					G12R	CD4 IFNg+ IL2+ TNFa+	
					G12D	CD4 IFNg+ IL2+ TNFa- CD4	
					G12V	IFNg+ IL2- TNFa+ CD4	
					G12C	IFNg+ IL2- TNFa- CD4	
					G12A	IFNg- IL2+ TNFa+ CD4	
					G12S	IFNg- IL2+ TNFa- CD4	
					G13D	IFNg- IL2- TNFa+ CD4	
					WT	IFNg- IL2- TNFa- CD8 T cells	
					Positive control		
					Master Mix		

*Elicio Therapeutics, Inc.*  
*Addendum: Immunogenicity and ctDNA Analysis Plan, Protocol ELI-002-001*  
*February 6, 2023, Version 1.0*

KRAS / NRAS						Change from	Fold change from
Patient ID	Mutation	Visit	Date	Antigen	Test	Result	baseline baseline
							CD8 IFNg
							CD8 IL2
							CD8 TNFa
							CD8 Cm
							CD8 Cm IFNg
							CD8 Cm IL2
							CD8 Cm TNFa
							CD8 Em
							CD8 Em IFNg
							CD8 Em IL2
							CD8 Em TNFa
							CD8 Naïve
							CD8 Naïve IFNg
							CD8 Naïve IL2
							CD8 Naïve TNFa
							CD8 TEMRA
							CD8 TEMRA IFNg
							CD8 TEMRA IL2
							CD8 TEMRA TNFa
							CD8 IFNg-
							CD8 IL2-
							CD8 TNFa-
							CD8 IFNg+ IL2+ TNFa+
							CD8 IFNg+ IL2+ TNFa-
							CD8 IFNg+ IL2- TNFa+
							CD8 IFNg+ IL2- TNFa-
							CD8 IFNg- IL2+ TNFa+
							CD8 IFNg- IL2+ TNFa-
							CD8 IFNg- IL2- TNFa+
							CD8 IFNg- IL2- TNFa-
							CD4 1+
							CD4 2+
							CD4 3+
							CD4 % 1+
							CD4 % 2+
							CD4 % 3+
							CD8 1+
							CD8 2+
							CD8 3+
							CD8 % 1+
							CD8 % 2+
							CD8 % 3+

Protocol ELI-002-001

Elicio Therapeutics, Inc

Confidential

Page 1 of x

Listing 4

In Vitro Intracellular Cytokine Staining

---

Repeat Layout used in listing 3 with IVS ICS.

Protocol ELI-002-001                      Elicio Therapeutics, Inc                      Confidential                      Page 1 of x

Listing 5  
 Ex Vivo Dexramer + T cell

Patient		Visit/ Week		Change from		Fold change from	
ID	KRAS/ NRAS (1)	Date	Dexramer	Test	Result(2)	baseline	baseline
					see note	% Viable cells	
						% Lymphocytes	
						% CD3 T cells	
						% CD8 T cells	
						% CD8+ Dexramer+	
						cells	
						% CD4 T cells	
						% CD4+ Dexramer+	
						cells	

Dextramers will include:  
 A11:01 G12V-10, A11:01 G12V-9, A11:01 G12D-10  
 A11:01 G12D-9, A03:01 G12V-10, A03:01 G12D-10, C08:02 G12D-10  
 C08:02 G12D-9, B07:02 G12R-10, A02:01 G12D-10, A02:01 G12V-10

Listing 6 In Vitro Dextramer

Repeat layout for listing 6 using IVS dextramer.

Protocol ELI-002-001                      Elicio Therapeutics, Inc                      Confidential                      Page 1 of x

Listing 7  
 ctDNA – Signatera Assay

Dose Cohort

Patient	Result	Change from	Fold change from	Fold change from	Doubling	Response	Duration of					
ID	Mutation	Visit	Date	Status	Type	Result	baseline	baseline	previous*	Time	e (1)	Response
						Negative/ Positive / Not performed	MTM/mL	VAF		--	--	--

Abbreviation: VAF = Variant Allele Frequency, MTM= mean Tumor Molecules

\*Indicates 2-fold or greater change.

(1) response is defined as decrease from baseline or undetectable value. (2) Duration is calculated as the date of the first response until the date where the ctDNA is detectable or greater than baseline value. (3) Doubling time is the time until the ctDNA has increase 2-fold from nadir.

## 5. R CODE FOR DFR(2X)

```
require(DT)
require(readxl)
require(ggplot2)
require(dplyr)
X13 <- read_excel("<filename.xlsx",
                 sheet = "Sheet4")
#View(X13May2022_Preliminary_ex_vivo_FS_data_for_Veristat_Dataset_to_R_)

datatable(X13,extensions = 'Buttons', filter='top',
          options = list(dom='Bfirtip',
                        lengthMenu = list(c(15, -1), c('15', 'All')),
                        buttons=c('copy', 'csv', 'excel', 'print', 'pdf'))))

GRb=subset(X13, assay=='GrB'&Antigen != 'CD3' )
IFN=subset(X13, assay=='IFNg'&Antigen != 'CD3' )
#p=ggplot(IFN, aes(x=Visit, y=Mean, color=Antigen ))

IFN = rename(IFN, id=Subject, day = Visit, antigen = Antigen, a1=Rep_1, a2=Rep_2, a3=Rep_3)
elsdfr2x(IFN, 3,3, "NS", ho.c=log10(2))
d=elsdfr2x (GRb, 3, 3, "NS", ho.c=log10(2), alpha=0.1, B=1000 )
```

```
impose.mono <- function(x, dir){
  # Function to impose monotonicity on elements of the vector, x
  # dir="incr" gives increasing monotonicity
  # dir="decr" gives decreasing monotonicity

  if(dir=="decr"){ x <- rev(x) }
  for(i in 2:length(x)){
    idx <- is.na(x[(i-1):i])
    if (sum(idx)==1){
      x[i] <- x[(i-1):i][!idx]
    } else {
      x[i] <- max(x[i-1],x[i])
    }
  }
  if(dir=="decr"){ x <- rev(x) }
  x
}

perm <- function(dat, nExp, nCtl){
  N <- nExp+nCtl      # total number of exp and neg ctl wells
  k <- NROW(dat)      # number of peptide pools
  B <- choose(N,nExp) # number of perms needed for complete enumeration

  if(B < 20) stop("Too few replicates to use this method (B < 20).")

  mu.e <- rowMeans(dat[,1:nExp], na.rm=TRUE)    # vector of peptide pool means
  mu.c <- rowMeans(dat[,nExp+(1:nCtl)], na.rm=TRUE) # vector of neg ctl means
```

```
